Online questionnaires will be used throughout the study. All the measures will be completed at baseline, T1 (post-intervention for experimental group), T2 (post-intervention for the control group and at two-month follow-up for the experimental group). To have a measure of the control group 2 months post intervention, participants completed further outcome measures at T3. For data analysis purposes the T3 results for the control group and those at T2 for the experimental group will be compared in order to assess the invention effect at same experimental time point for both groups (i.e., 2 months post intervention). To maximize retention, 3 electronic reminders will be sent to participants who had not completed questionnaires, on the 3 consecutive days after the release of the questionnaire. A further reminder will be sent out via email and text message. If questionnaires will be still not completed participants will be telephoned to encourage questionnaire completion. Participants will be also phoned after completing the intervention to discuss the progress they had made and share their questionnaire results.

Statistical Analysis Plan

Statistical analyses will be performed using the Statistical Package for Social Sciences (SPSS) version 26.0. All statistical tests will be 2- tailed with an alpha set to .05. To account for missing data from participants not completing the post-intervention or follow-up intervention analysis an imputation analysis will be undertaken. Missing data will be handled through multiple imputation using the *Markov Chain Monte Carlo* approach (Jakobsen et al.,

2017). For comparison, a complete case analysis will be also performed by analyzing only the completed questionnaire data without imputing missing data. As there will be substantial differences, statistical analysis using the imputed data are reported in the results section.

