The primary study outcome will be a change in TFI score between the groups at postintervention (T1). A difference in scores between T1–T2 for the experimental group will be used to assess the stability of intervention effects. According to recommendations for statistical analysis of internet interventions effect sizes, linear mixed effects models, and the reliable change index will be used to assess the primary and secondary outcomes (Hesser, 2015). Changes from baseline to post-intervention will be compared within and between groups using the pre-post-test effect size (Cohen's *d*) for all primary and secondary outcomes using the observed data. Effect sizes of d = 0.20 represent small effect sizes; those of d =0.50, medium effect sizes; and those equal or greater than d = 0.80, large effect sizes (Cohen, 1992).

A Linear Mixed Model (LMM), which provides unbiased results in the presence of missing data (using all available data), will be applied to analyze the intervention effect over time for each outcome measure. An unstructured-repeated effects and identify-random effects covariance structure provided the best model fit based on the Akaike's Information Criterion (AIC). Time will be treated as a repeated and fixed effect. Restricted maximum likelihood estimation will be applied. The Type III F test sums of squares from the LMM will be calculated. As a sensitivity analysis, baseline tinnitus severity will be initially added as a covariate, but as it had no significant effect on the results it will be removed from the model.

Another model will be run to test the differences during the course of the 8 weeks intervention for the weekly outcome measures. Post hoc time comparison will be carried out in the case of significant group differences to assess at which time points these differences occurred.

In addition to statistical significant, clinical significance will also reported. A 13 point difference is recommended by the original developers of the TFI (Meikle et al, 2012) to indicate a meaningful change in scores. To handle study variability, the reliable change index (RCI) (Jacobson & Truax, 1991) is recommended as a means of calculating clinical significance for the TFI as the primary outcome. This will be calculated using the mean pretest-posttest score difference, the pretreatment standard deviation (17.49), and a test-retest reliability coefficient of 0.78, and as reported in the validation study

Sample Characteristics

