Descriptive statistics including gender, age, ethnicity, race, tinnitus duration, hearing aid use, and professionals consulted, ease of computer use, veteran status, education and employment status will be used to describe the sample. The means and standard deviations will be reported for each outcome measure at each time point. Descriptive statistics will be also used to describe the sample and intervention engagement including the number of logins and modules read. A Chi square test of independence will be used to identify group differences regarding engagement and compliance rates.

Dimension	Outcome Measures	Internal consistency	Range of scores	Levels of significance	Timeframe : T0 (baseline)	Timeframe: T1	Timeframe: T2	Timefra me: T3
Explanation						Post- intervention for the experimental group; post weekly monitoring for the control group	2 month follow-up for experiment al group, postinterve ntion for the control group	2 month follow-up for the control group
Tinnitus distress	Tinnitus Functional Index (TFI; Meikle et al, 2012)	.97	0-100 A reduction of scores indicates improvement	>25= mild (no need for intervention) 26-50= significant (possible need for intervention) 50+ =severe (need for a more intense	Both groups x	Both groups	Both groups	Control group only x
Generalized Anxiety	Generalized Anxiety Disorder (GAD-7, Spitzer, Kroenke, Williams, et al., 2006)	.89	0-21 A reduction of scores indicates improvement	intervention) 0-4= minimal anxiety 5-9= mild anxiety 10-14= moderate anxiety 5-21= severe anxiety	X	x	x	x

Table 1. Study outcome measures used pre-intervention, post-intervention and at 2-months follow-up

Depression	Patient Health Questionnai re (PHQ-9; Spitzer, Kroenke	.83	0-27 A reduction of scores indicates improvement	5-9=mild depression 10-14=moderate 15-19=moderately severe 20-18= severe depression	x	X	X	x
	Williams, 1999)							
Insomnia	Insomnia Severity Index (ISI; Bastien, Vallières, & Morin, 2001)	.74	0-28 A reduction of scores indicates improvement	0-7 = Not clinically signi 8-14 = Subthreshold inso 15-21 = Clinical insomnia (moderate severity) 22-28 = Clinical insomnia (severe degree)	X	Х	X	X
Tinnitus Cognitions	Tinnitus Cognitions Questionnai re (TCQ; Wilson & Henry, 1998)	.91	0-104 A reduction of scores indicates improvement	Higher scores indicate a greater tendency to engage in negative cognitions in response to tinnitus	X	Х	X	X

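### Whether baseline TFI stays in the primary mixed model is decided by the results, and no stated model is fixed that uses baseline efficiently

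*Combined protocol and SAP*

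**What the plan says.** The Statistical Analysis Plan section defines the primary contrast: "The primary study outcome will be a change in TFI score between the groups at postintervention (T1"). A linear mixed model "will be applied to analyze the intervention effect over time for each outcome measure". On its terms, the section says "Time will be treated as a repeated and fixed effect"; it names neither arm nor arm-by-time. The covariance is unstructured for the repeated effects, with an identity random-effects structure, reported as chosen on AIC.

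On baseline, the section says "As a sensitivity analysis, baseline tinnitus severity will be initially added as a covariate, but as it had no significant effect on the results", and then "it will be removed from the model".

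Baseline is also a measurement time. Questionnaire Administration says "All the measures will be completed at baseline, T1 (post-intervention for experimental group), T2", and Table 1 lists T0 for both groups. No section says whether T0 is an outcome row in the mixed model, or whether the arms share a baseline mean.

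The Randomization section that follows the sample size section stratifies allocation by language (English or Spanish). Neither the main mixed model nor the weekly-outcome model mentions language.

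**The concern.** There are two separate problems.

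First, the rule for baseline depends on results. Baseline is adjusted for because it predicts the outcome and so sharpens the treatment contrast. That decision belongs in the plan before outcomes are seen. A non-significant covariate, or a treatment result that did not move, is not a reason to take it out.

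Second, the model is not specified well enough to show how baseline enters. Three readings are open, with different precision for the primary T1 effect:
- T0 is an outcome row with free arm means.
- T0 is an outcome row with a common mean across arms.
- Only post-baseline scores are outcomes.

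On the first and third readings, the 95% confidence interval would be wider than the collected data require.

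**Working it through.** **Inputs**
- n = 58 per arm (Sample Size, Power and Attrition). The plan's inflation reproduces: 58/0.8 = 72.5, rounded up to 73 per arm, 146 in total.
- Baseline SD s0 = 17.49 and test-retest coefficient 0.78 (Statistical Analysis Plan). Both are given for the reliable change index, not for this model. Here 17.49 is an assumed scale and 0.78 an upper anchor for the T0–T1 correlation ρ.
- d = 0.50 (sample size section). On the assumed scale this is 0.5 × 17.49 = 8.745 points.
- Assumptions: ρ = 0.5, 0.6 or 0.78; SD ratio s1/s0 = 1.0 or 1.2; complete data. A ratio above 1 is plausible because entry requires a TFI of at least 25.

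The plan gives no variance, interval width or power for the mixed-model contrast, so there is no such figure to reproduce.

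**Step 1: what each T0-row model estimates.** With complete data and unstructured covariance, free arm-by-time means make the T1 effect equal to the difference in mean change. Constraining the baseline means to be equal makes it equal to the baseline-adjusted difference. In one simulated three-occasion dataset with 58 per arm, the first pair agreed at −6.870 and the second at −8.456.

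**Step 2: variances per participant**
- Change score: s0² + s1² − 2ρ·s0·s1
- Baseline-adjusted: s1²(1 − ρ²)
- Difference: (s0 − ρ·s1)², never negative

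The half-width is t(114 df) × √(2V/58), with t about 1.981. For ρ = 0.5 and equal SDs, change V = 305.9, SE = √(2 × 305.9/58) = 3.25, half-width 6.43. Adjusted V = 0.75 × 305.9 = 229.4, SE 2.81, half-width 5.57.

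| s1/s0 | ρ | Variance ratio, change to adjusted | Half-width, change → adjusted (points) | n per arm for equal precision (58/ratio) | Power at 8.745 points, change → adjusted |
|---|---|---|---|---|---|
| 1.0 | 0.5 | 1.333 | 6.43 → 5.57 | 44 | 76.1% → 86.9% |
| 1.0 | 0.6 | 1.250 | 5.75 → 5.15 | 47 | 84.7% → 91.6% |
| 1.0 | 0.78 | 1.124 | 4.27 → 4.03 | 52 | 98.1% → 98.9% |
| 1.2 | 0.5 | 1.148 | 7.16 → 6.69 | 51 | 66.9% → 72.9% |
| 1.2 | 0.6 | 1.085 | 6.43 → 6.18 | 54 | 76.1% → 79.4% |
| 1.2 | 0.78 | 1.007 | 4.85 → 4.83 | 58 | 94.3% → 94.5% |

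If the true between-arm difference were 13 points (an assumption), power at ρ = 0.5 would go from 97.8% to 99.6% with equal SDs and from 94.6% to about 97% at ratio 1.2. The gain is then mainly a narrower interval.

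Simulation (8,000 trials per setting, true effect −8.745) gave means of −8.71 to −8.78 for both estimators, so both are unbiased. The variance ratios were 1.33, 1.25 and 1.12 (equal SDs) and 1.15, 1.08 and 1.00 (ratio 1.2).

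**Step 3: the other readings.** With post-baseline outcomes only and no baseline term, the ratio to the adjusted variance is s1²/[s1²(1 − ρ²)] = 1/(1 − ρ²), which is 1.33, 1.56 and 2.55 at ρ = 0.5, 0.6 and 0.78. The excess is 33%, 56% and 155%, whatever the SD ratio. With a common baseline mean the excess is zero.

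**Step 4: what the covariate check could show.** Suppose T0 is an outcome row and is also entered as a covariate with coefficient b. The determinant of the residual covariance then scales with (1 − b)². With 2 × 58 = 116 participants, the log-likelihood rises by 116·ln(1/|1 − b|): 267 at b = 0.9, 801 at b = 0.999, and without bound. That fit is degenerate and cannot guide the choice of model.

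**The case against.** **The covariate was only a sensitivity analysis.** The unadjusted model may always have been the primary one, and the sentence may mean that the treatment result did not change rather than that the covariate had a large p-value. Either is possible. But the stated consequence is removal from the model, not reporting beside it, and both meanings rest on results.

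**The covariate's removal does not cause the change-score loss.** A reader might infer that dropping it costs the 12% to 33%. The documents do not support that: where T0 is an outcome row, the loss comes from free baseline means, and adding T0 as a covariate would not repair it. The two problems must stay separate.

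**The outcome-row reading is unconfirmed.** It fits a change outcome analysed over time. However, an ordinary result from the covariate check is hard to square with the degenerate fit in Step 4. That leaves post-baseline outcomes, or change scores, as live alternatives. This objection stands, so the size is given for each reading.

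**The figures rest on assumptions.** The correlation, SD ratio, 58 complete cases per arm and 17.49 as the scale for d = 0.50 are not established for this model; the plan recruits 73 per arm and reports multiply imputed data. Holding ρ fixed at ratio 1.2 is also a choice. If the entry cut-off narrows the baseline SD while slope and residual SD stay fixed, starting from equal SDs, the excess at ratio 1.2 is 21%, 15% and 6% (residual-based formula: (1 − ρ)²/(1.44 − ρ²)) for starting ρ of 0.5, 0.6 and 0.78. These figures still lie below the equal-SD values.

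**Language may simply be unmentioned.** A reader might infer that it was deliberately excluded. The list of model terms is partial, with arm itself missing, so silence does not show that.

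**Conclusion.** The point holds as a specification and efficiency concern. The results-based removal is unsound on any reading and needs no numerical assumption. The precision cost is conditional on the assumptions listed above:
- **T0 row with free arm means:** about 12% to 33% excess variance for ρ of 0.78 to 0.5 with equal SDs, and about 1% to 15% at SD ratio 1.2.
- **Post-baseline outcomes without baseline:** 33% to 155% for ρ of 0.5 to 0.78.
- **Baseline means constrained equal:** nil, and only the wording needs correcting.

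Two stronger conclusions are tempting and not supported. One is that the primary estimate is biased; under randomisation the change-score contrast is unbiased. The other is that outcomes had certainly been analysed when this was written. The past-tense wording on the covariate and on AIC suggests it, but the document mixes tenses throughout.

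For language, the documents give neither the Spanish-speaking share nor the effect of language, so no gain can be derived. The plan should be changed on this point, but it does not invalidate the trial.

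**What to change.** Delete the results-based removal and state one primary model, using either:
1. Post-baseline TFI as outcome, with arm, time, arm-by-time, baseline TFI, baseline-by-time and language; or
2. T0 as an outcome row with baseline means constrained equal across arms, plus language, and T0 not also entered as a covariate.

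Keep these terms whatever their p-values. Specify the same model for each secondary outcome, with that outcome's own baseline. Include language because randomisation is stratified on it, without claiming a precision gain. Report the unadjusted model as the sensitivity analysis.

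The cost is wording and model terms only; all the data are already planned for collection. If outcome data have been seen, label the change post hoc and report both estimates.

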- Participants with a score of 15 or more on the PHQ-9 or indicated self-harm on question 10 will receive a phone consultation from a clinical psychologist on the research team. This call will ensure that they are under care elsewhere or necessary resources and/or referrals can be provided.

Recruitment Strategy

Recruited will involve many strategies including a television broadcast, promoting the study via tinnitus support groups in Texas and the American Tinnitus Association (ATA), and contracting the company "TrialFacts" to boost recruitment. Further recruitment strategies will involve the use of social media (e.g., Facebook and Twitter). Flyers and posters will be distributed to local communities and put up in clinic waiting rooms. Professionals such as audiologists and otolaryngologists in the state of Texas will be notified about the study and provided with leaflets to distribute to suitable patients. Those interested will be directed to the study website (www.tacklingtinnitus.org) where they can read more about the study and register their interest in study participation. Following registration, they will be invited to complete the screening questionnaire. They will be informed of their right to withdraw without penalty at any stage of the process.

Sample Size, Power and Attrition

Sample size estimation will be calculated using G*Power version 3.1.6 (Faul et al., 2007) and based on achieving a 13-point clinically meaning change between baseline and post-intervention using the primary assessment measure, the TFI. Pilot data (Beukes et al., Submitted) indicated 26 participants per group with a 1:1 allocation to achieve 80% power to detect a between-group mean standardized difference effect size of d = 0.50 (a moderate effect size). As this will be fewer than the 58 participants suggested using data from previous RCTs of this intervention, (Beukes et al., 2018) we selected 58 per group. In addition, sample size will be inflated to account for missing data, estimated to be 20% from the US phase I trial data (Beukes et al., 2021b). The aim will be thus to recruit 146 participants with 73 in each arm (calculated as 58/0.8).

Randomization

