Guidance will be provided to support participants while undertaking the intervention. This will include monitoring progress, monitoring weekly scores, providing feedback on worksheets completed, outlining the content of new modules, and answering questions.

Outcome Measures

Primary Outcome Measure

The primary outcome measure will be tinnitus severity as measured by the Tinnitus Functional Index (TFI; Meikle et al., 2012). The TFI has been translated into more than 15 languages and been validated for several populations including Chinese, Dutch, Swedish and German (Henry et al., 2016). It will be selected over other tinnitus questionnaires as it will be specifically developed to measure tinnitus severity and assess responsiveness to treatment and for comparison purposes with previous trials (e.g., Beukes et al., 2018). Meikle et al. (2012) reported that meaningful changes occur when scores are reduced by 13 points or more.

Secondary Outcome Measures

Secondary outcome measures will assess anxiety, depression, insomnia, tinnitus cognitions, hearing-related difficulties, and health-related quality of life, as shown in Table 1. To reduce the assessment load, the Tinnitus and Hearing Survey (THS; Henry, et al., 2015) will be used

to identify hearing disability and hyperacusis as it only includes 10 questions. The section on tinnitus also served as a secondary tinnitus measure. The EQ-5D-5L (Herdman, et al., 2011) will be selected to measure general health-related quality of life. All questionnaires will be used with the required permissions and agreements will be set up for those that are not freely available to use. For Spanish speakers, validated Spanish translated versions will be used. Where these will be unavailable, validated translations will be undertaken (Manchaiah, et al., 2020b).

Weekly Monitoring During the Intervention

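### The reliable change index is defined on the mean change, but its stated inputs give one person's error, so as written it cannot show who reliably changed

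*Combined protocol and SAP*

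**What the plan says.** The Statistical Analysis Plan section says that clinical significance will be reported alongside statistical significance, and it brings in two criteria.

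- The first is a fixed benchmark: "A 13 point difference is recommended by the original developers of the TFI". The Primary Outcome Measure section has the same figure: "meaningful changes occur when scores are reduced by 13 points or more". The Sample Size, Power and Attrition section also uses it: the calculation is "based on achieving a 13-point clinically meaning change between baseline and post-intervention".
- The second is the Jacobson-Truax reliable change index, which "is recommended as a means of calculating clinical significance for the TFI as the primary outcome". Its ingredients are then listed: "This will be calculated using the mean pretest-posttest score difference, the pretreatment standard deviation (17.49), and a test-retest reliability coefficient of 0.78".

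No cut-off for the index appears, and no resulting threshold in TFI points. Nothing says that each participant will be classified. The plan also does not say whether the 13 points apply to individuals or to group means.

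**The concern.** The index divides a change by the standard error of a difference score. A standard deviation and a test-retest reliability give that error for a single person, so the change above it must also be a single person's. The plan names the mean change instead.

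An analyst who followed the text would produce one figure per arm that cannot be read as a responder rate. It cannot be read as a test of the arm's mean either, because the divisor does not shrink as participants are added. The question the index exists to answer, how many people changed by more than measurement error, would go unanswered. If the arm-level figure were set against the usual cut-off, a whole arm could be labelled reliably changed, or not, on a comparison that has no meaning.

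**Working it through.** **Inputs.** Pretreatment SD 17.49 and test-retest reliability 0.78 (Statistical Analysis Plan); 13-point benchmark (same section and Primary Outcome Measure); two-tailed alpha of 0.05 (Statistical Analysis Plan); lowest eligible TFI score 25 (Study eligibility). The multiplier 1.96 is an assumption that matches this alpha. The plan gives no threshold or standard error of its own to reproduce.

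**Error of one person's change**

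- Standard error of measurement = SD × √(1 − reliability) = 17.49 × √0.22 = 8.20.
- Standard error of a difference = √2 × 8.20 = 11.60.
- Individual threshold = 1.96 × 11.60 = 22.74 points (from unrounded values).

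**With the mean as numerator.** Index = mean change / 11.60.

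- Mean change 13: 13 / 11.60 = 1.12.
- Mean change 20: 20 / 11.60 = 1.72.
- Mean change 25: 25 / 11.60 = 2.15.

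These figures say nothing about how many participants changed. To illustrate, assume normally distributed changes. With a mean of 13 the index is 1.12 whatever the spread, yet the proportion at or above 22.74 is 21%, 29% or 33% for an SD of change of 12, 17.49 or 22. With a mean of 25 the index is 2.15, above 1.96, yet only 54% to 58% of participants pass 22.74 over the same SDs.

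The divisor is also wrong for a mean. With 58 participants and independent errors, measurement error contributes 11.60 / √58 = 1.52 points to the standard error of the mean change, not 11.60.

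**The 13-point benchmark beside the individual threshold**

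- One person's 13-point change gives an index of 13 / 11.60 = 1.12. With normal errors and no true change, P(Z > 1.12) = 0.13, so about 13% of unchanged participants would pass 13 points. At 22.74 the figure is 2.5%.
- The ordering does not depend on 1.96: a 90% multiplier gives 1.645 × 11.60 = 19.1 and an 80% multiplier 1.2816 × 11.60 = 14.9, both above 13.
- Illustration with an assumed mean change of 13 and SD of change of 15: 50% reach 13 points and 26% reach 22.74.

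**Reach of the threshold.** A participant who enters at 25 must fall by 22.74 / 25 = 91% to count as reliably improved.

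**The case against.** The strongest reply is that this is loose wording. The plan cites the Jacobson-Truax method, which works on individual change, and lists its usual inputs without writing out a formula. That may well be what was intended. But the numerator is stated, and no other section mentions classifying participants or counting those who changed, so nothing corrects it. The last sentence of the paragraph stops without a full stop after a reference to the validation study, so a cut-off or citation may have been lost there. The numerator wording comes earlier in the sentence and is intact.

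A reader might infer something stronger: that the 13-point rule and the index contradict each other, so that the clinical-significance result must be wrong whichever is used. The documents do not support that. A benchmark for whether a change matters may lie below a threshold for whether one person's change exceeds measurement error. If the 13 points are a group benchmark, individual error does not apply to them. The plan also names the index as its means of calculating clinical significance, which suggests that it governs. Nor does the plan say that an arm improving by 13 points would be called not reliably changed, since it states no cut-off.

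Two further points stand. The 13% false-improvement rate would act in both randomised arms, so it does not by itself invalidate a comparison between them. And clinical significance is additional reporting, so the stakes are limited.

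**Conclusion.** The definition of the index needs correcting. As written it pairs a group mean with an individual's standard error and yields one uninterpretable number per arm, such as 1.12 for a mean change of 13, with no proportion reliably changed.

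The 11.60-point error follows directly from the plan's SD and reliability. The 22.74-point threshold also needs the assumed 1.96, and the 13% and 2.5% rates need normal errors. The responder proportions are illustrations with assumed means and SDs of change, not predictions for this trial.

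The effect is confined to the clinical-significance reporting. The mixed-model comparison of TFI between arms at T1 does not use the index. The 13-point benchmark is not an error; it needs only to be reported as a separate quantity.

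**What to change.** In the sentence that begins "This will be calculated using the mean pretest-posttest score difference", replace the mean with each participant's own T0 minus T1 TFI difference. Then:

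1. Divide each difference by 11.60 and state the cut-off. With 1.96, a fall of 22.74 points or more is reliably improved, a rise of 22.74 or more is reliably worse, and anything between is unchanged.
2. Report the three proportions by randomised arm at T1. A risk difference with a 95% confidence interval for the proportion improved would be a useful addition.
3. Report the proportion with a fall of 13 points or more separately as meaningful change. Note that it answers a different question and lies below the individual reliable-change threshold.
4. The same section says the index will be used for primary and secondary outcomes but gives inputs only for the TFI. Either supply the others or limit the index to the TFI.

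The cost is a few lines of text and one table, with no new data. There are two drawbacks. The reported responder rate will be lower than under the 13-point rule. Participants with low baseline scores can hardly reach the threshold, so the table should carry a note saying so.

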Participants meeting the inclusion criteria will be randomly assigned in the ratio of 1:1 and enrolled to either the experimental or control group using a computer-generated randomization scheduled by an independent research assistant in blocks of varying sizes after participants are pre-stratified for language (English and Spanish).

Patient Public Partnership (PPI)

A PPI will be established to include two individuals with tinnitus who had piloted the ICBT intervention, two audiologists, two researchers. Meetings will be held via video conferencing. The aim of the PPI will be to guide the study processes and input into the research strategy to boost recruitment and other elements of the study to ensure high compliance and engagement.

Intervention

The ICBT intervention content will be based on a CBT self-help program originally developed in Swedish (Andersson & Kaldo, 2004) and later adapted and translated in English (Abbott, et al., 2009). The intervention will be subsequently transformed into an 8-week interactive e-learning version suitable for a UK population (Beukes, et al., 2016) and then adapted linguistically and culturally to ensure suitability for a US population (Beukes, et al., 2020). These adaptions prioritized accessibility of the intervention, such as lowering the readability to below the recommended 6th-grade level, as more than half the US adult population have low literacy skills (Statistics, 2003). The intervention will be augmented by a module on mindfulness and more videos. The ICBT platform in the US application consisted of 22 modules with worksheets and quizzes (see Beukes et al., 2020; Beukes et al., 2021a for more details).

The intervention platform will be transferred from Sweden and housed in the US (Lamar University) to comply with the needed US data protection regulations. Prior to this feasibility trial, acceptability and functionality of this intervention for a US population will be first ensured (Manchaiah et al., 2020). Further details about the features, functionalities, and intervention components are presented in Manchaiah et al. (2020).

Both groups will received the same intervention, only the timings regarding receiving the intervention will vary. The control group will receive the experimental intervention 8 weeks after the experimental group commenced the program.

Audiology Guidance

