Throughout the program, participants will be monitored weekly by means of the Tinnitus Handicap Inventory, Screening version (THI-S). The THI-S consists of a 10-item questionnaire and scores are comparable (r = .90) with the full version of the THI (Newman et al, 2008). The weekly scores will be also used to detect possible adverse effects. If scores increased by more than 10 points between two consecutive weeks, this will be noted as an adverse effect. Those indicating adverse effects will be contacted to address the identified problems. Participants will be also monitored by a newly developed Tinnitus Qualities Questionnaire (TQQ; Beukes et al., 2021a). The TQQ measures tinnitus qualities such as pitch, loudness, and the number of tones heard. The scores of TQQ can range between 0 to 100 with higher scores indicating more problematic tinnitus.

Intervention Variables

Intervention compliance will be assessed by determining retention rates and compliance in completing outcome questionnaires. Intervention engagement will be assessed by the number of logins, the number of modules read, and the number of messages sent during the intervention. Adverse effects will be monitored by 1) Direct questioning in the outcome questionnaire regarding the presence of adverse effects 2) Adverse effects written in messages or worksheets 3) An increase of 10 points or more during weekly monitoring using the THI-S questionnaire.

Questionnaire Administration

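### Engagement is measured as per-person counts, but its only planned test is a chi-square with no cut-point: error rate held, power lost

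*Combined protocol and SAP*

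**What the plan says.** The combined protocol and SAP deals with engagement in two places.

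- **Intervention Variables** defines the measures: "Intervention engagement will be assessed by the number of logins, the number of modules read, and the number of messages sent during the intervention". Compliance is defined separately: "Intervention compliance will be assessed by determining retention rates and compliance in completing outcome questionnaires".
- **Sample Characteristics** gives the analysis. It first commits to description: "Descriptive statistics will be also used to describe the sample and intervention engagement including the number of logins and modules read". It then names one test, for engagement and compliance together: "A Chi square test of independence will be used to identify group differences regarding engagement and compliance rates".

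No t-test, rank test or count model is named for engagement. The mixed models in the Statistical Analysis Plan section cover the outcome measures and the weekly measures, not engagement. The document does not say how a count becomes a category, or what an engagement rate is.

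**The concern.** A chi-square test of independence needs one categorical response per independent participant. Retention and questionnaire completion supply that, since each is yes or no per person. Logins, modules read and messages do not. They have to be put into categories first, and the plan leaves that step open.

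Two things are at stake. First, categorising a count throws away order and distance, so a real difference in engagement is more easily missed. Second, a cut-point that is not fixed in advance can be chosen after the data are seen.

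Both groups eventually receive the programme, so this test would compare engagement under immediate and delayed delivery. A reader may use that comparison when judging the control group's later results, although the plan itself makes no conclusion depend on it.

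**Working it through.** **Inputs from the document**
- Group size: 58/0.8 = 72.5, rounded up to 73 per arm and 146 in total (Sample Size, Power and Attrition). The plan's figure reproduces.
- Alpha 0.05, two-sided (Statistical Analysis Plan).
- At most 22 modules per person (Intervention).
- d = 0.50, which the plan uses for the TFI. It is borrowed here for illustration only.

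**Inputs assumed.** The document gives no mean, SD, within-person correlation or expected difference for engagement, and no power target for this comparison. The values below are therefore illustrations across a range.

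**Step 1. Error rate with one entry per participant.** Counts were simulated with no true difference and 73 per arm. A median-split 2×2 table rejected in 4.6–6.4% of trials. A full cross-table of count values rejected in 0.8–2.4%, below nominal because the cells are sparse. With modules cross-tabulated by value there are about 21 degrees of freedom, and about 79% of expected cells are below 5. Neither form inflates the error rate to any important degree.

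**Step 2. Power, closed form, normal variable, d = 0.50.**
- Comparison of means: Φ(0.5 × √(73/2) − 1.96) = Φ(3.02 − 1.96) = Φ(1.06) = 86%.
- Median split: the proportions above the cut are Φ(0.25) = 0.599 and 0.401, a difference of 0.197. The standard error is √(2 × 0.25/73) = 0.0828 under the null and √(2 × 0.599 × 0.401/73) = 0.0811 under the alternative. Power = Φ((0.197 − 1.96 × 0.0828)/0.0811) = Φ(0.43) = 67%.
- The number per arm for 80% power rises from 63 to 100.

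**Step 3. Power, simulated overdispersed counts, assumed 1.4-fold difference, 73 per arm.**

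| Assumed count | Rank test | Median split |
|---|---|---|
| Mean 20, SD 15 | about 68% | about 54% |
| Mean 11, SD 7 | about 82% | about 69% |
| Mean 20, SD 10 | about 97% | about 90% |

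Repeat runs differ by a few points. Taken together they give about 68–96% for the rank test, 53–90% for the median split and 2–27% for a cross-table of raw counts.

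**Step 4. A second set of assumptions, shift of d = 0.50, 73 per arm.** For modules (mean 11 of 22, within-person correlation 0.3), power is 87% by rank test, 70% by median split and 30% by cross-table. For logins (mean 15, variance/mean 8), it is 66%, 52% and 4%.

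**Step 5. The one route to an inflated error rate.** Suppose each of a person's 22 modules were entered as a separate read/unread observation. With within-person correlation ρ, the variance is multiplied by D = 1 + 21ρ, and the actual error rate is 2 × (1 − Φ(1.96/√D)).
- ρ = 0.05: D = 2.05, error 17%.
- ρ = 0.10: D = 3.10, error 27%.
- ρ = 0.30: D = 7.30, error 47%.

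Simulation agrees (17%, 27% and 46–47%). Nothing in the document says the modules will be pooled in this way.

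**The case against.** The strongest defence is the wording. The test is for rates, and a rate put into a test of independence is most naturally a proportion of participants. On that reading the test is valid, and the counts themselves are still reported descriptively, so the data are not lost. The plan sets no power target here, engagement is in none of the three study objectives, and the test sits under Sample Characteristics. The primary comparison is the TFI at T1, before the control group starts the programme.

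Most of this stands. The reading is plausible, the error rate is then sound, and the importance is limited. It does not remove the point, because a proportion engaged needs a threshold and none is given for logins, modules or messages. The descriptive summary does not replace an efficient between-group test. The size of the loss also depends on assumed inputs: at mean 20 and SD 10 the split still has about 90% power.

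A reader might go further and infer that the planned test has a grossly inflated error rate. The document does not support that. Comparing the two arms' total logins or messages with an equal split would reject falsely far too often (17%, 38% and 54% at variance/mean of 2, 5 and 10), but that is a goodness-of-fit test and not the test of independence the plan names. Logins and messages have no denominator, so their totals alone cannot form the two-way table. Only modules could be pooled that way, and the plan does not say they will be.

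**Conclusion.** The point holds as a mismatch between measure and test, at low severity. The only test named for engagement needs categories, engagement is defined by counts, and no cut-point is given. With one entry per participant, the cost is power and an open choice of threshold, not false positives. In the settings tried, a median split costs roughly 7 to 20 percentage points against a test that uses the counts (97% to 90% at the mild end, 86% to 67% at d = 0.50). A raw cross-table has little power in any of them.

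These sizes rest on assumed distributions and assumed differences. The direction does not depend on any one of them. Error rates of 17–47% would apply only if module-level events were pooled across people at correlations of 0.05–0.30, and the plan does not state this. It would also be wrong to infer that the efficacy conclusions are at risk: the primary TFI analysis and the sample size do not use this test.

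**What to change.** Split the sentence in Sample Characteristics in two.

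- **Compliance:** keep the chi-square test, or Fisher's exact test if cells are small, for retention and questionnaire completion, with one yes/no value per participant.
- **Engagement:** compare logins, modules read and messages sent with one value per participant, by a Wilcoxon rank-sum test or negative binomial regression. Report the difference or rate ratio with a 95% CI. Modules read cannot exceed 22, so the rank test is the simpler choice for that measure.

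If a proportion engaged is also wanted, state its threshold before the data are examined and keep it as a supplement to the count comparison. The cost is a few lines of SAP wording. No new data, visits or participants are needed.
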